Most states do not have strong regulations for physical activity or screen-time in childcare settings. Louisiana's Department of Education (DOE) is implementing new regulations for children in childcare settings in 2015 to comply with national recommendations: 1) physical activity of at least 1 hour/day and 2) screen-time limited to 2 hours/day. The DOE is also providing extensive training and programmatic support to the centers. For the proposed project, the MHCI joins academic researchers at Pennington Biomedical to evaluate the implementation of these regulations and to

examine effects on children's health behaviors. During this project, we will answer three major questions: 1) are the regulations being implemented as intended; 2) do the policies benefit the intended audience; and 3) what do stakeholders identify as the most important strategies to improve children's health behaviors. The demographics of Baton Rouge provide an opportunity to examine these questions in a high risk population: 46% of city residents are non-Hispanic black and 28% of children under the age of 5 years live in households below the federal poverty level.

The aims of the project are:

**Specific Aim 2:** To examine the physical activity and screen-time behaviors of children enrolled in licensed childcare centers before and after the enactment of new state regulations.

*Through this academic-community partnership, we are taking advantage of a natural policy experiment to examine the childcare environment and children's behaviors before and after implementation of a policy change. We will also facilitate conversations among stakeholders to create additional strategies to increase young children's physical activity and decrease screen-time both in childcare centers and in other settings. The overall goal is to increase physical activity and reduce screen-time among preschoolers enrolled in childcare centers. If successful, we will disseminate findings throughout the Gulf States region as a model of how changing policies in childcare settings can improve children's health behaviors and reduce childhood obesity.*

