Reducing childhood obesity is identified as a top priority of the Mayor's Health City Initiative (MHCI) of Baton Rouge, which is a non-profit organization that brings together key stakeholders in the community to promote healthy living and active lifestyles. *Pennington Biomedical has joined with the MHCI to lead a number of projects to establish the prevalence of obesity and health risk factors in the community, to evaluate simulated effects of policy changes on childhood obesity prevalence, and to coordinate medical, academic, and non-profit organizations to strategize ways to promote healthy behaviors among children and families.* This proposal represents a step forward in the partnership between the MHCI and Pennington Biomedical to empirically test the effects of a health policy aimed at improving children's health behaviors in childcare settings. Given the vast majority of preschool children attend childcare centers, implementing policies that promote physical activity in these centers may have direct, impactful health benefits for young children.

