### A Carrot and Stick Approach to Improve Community Policies

Over the past year, the Louisiana Department of Education (DOE) has been given authority of childcare center licensing in the state of Louisiana. A 2012 state legislative mandate seeks to create a unified early childhood system under the DOE. With this transition, all licensing requirements are being revised; early care and education programs are being organized under local childcare center networks; new standards are being implemented for all childcare center providers that accept public funds; and a quality rating system is being redeveloped. Specific to the proposed project, new licensing standards will affect children attending over 1,300 licensed childcare centers state-wide and include: 1) physical activity of at least 1 hour/day and 2) screen-time prohibited for children younger than 2 years and limited to 2 hours/day for children over 2 years. Childcare centers in East Baton Rouge Parish must begin implementing changes by 2016 to renew their annual license.

In addition to the mandated regulations, the DOE is also offering new training and programmatic opportunities to help childcare centers achieve the regulations. The DOE has engaged directly with childcare centers around the state by supporting the implementation of the Nutrition and Physical Activity Self-Assessment for Child Care (NAP SACC) intervention, which is funded by the state's Maternal and Child Health Title V Block Grant and 1305 funding. NAP SACC is a national evidence-based intervention to prevent and reduce childhood obesity. It is implemented in childcare centers and is designed to promote healthy weight development in preschool children by improving the nutritional quality of food served, amount and quality of physical activity, staff-child interactions, nutrition and physical activity policies and practices, and related environmental characteristics. Over 200 centers have participated in the program and have integrated practices that support healthy weight behaviors since NAP SACC began in Louisiana in 2010. The Louisiana DOE will train childcare center personnel in East Baton Rouge Parish on these new regulations in 2015-16, offering a natural opportunity to examine childcare centers before and after implementation of the new policy.

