### **Primary Endpoints and Data Analysis Plan**

Primary endpoints will include 1) changes in objective child physical activity, as measured via 7-day accelerometer at baseline and 1 year, including minutes/day MVPA in childcare center, minutes/day MVPA total; 2) classroom observation of child screen-time, as measured with EPAO observation method to quantify average minutes/day screen-time in childcare center; and 3) parent reports of child screen time to quantify minutes/day screen-time total. Age, sex, BMI z-score, and sociodemographic characteristics will be included as covariates. We will also assess the cross-sectional and longitudinal associations among sedentary behavior (by screen-time observation/self-report and by accelerometry), physical activity (by accelerometry), and fundamental motor skills.

A repeated measures ANCOVA model will be used to test for effects of policy implementation on each dependent continuous variable (minutes/day MVPA in childcare center, minutes/day screen-time in childcare center, minutes/day MVPA total, minutes/day screen-time total). Covariates will include age, sex, BMI z-score, and sociodemographic characteristics. Correlations and a repeated measures ANCOVA will be used to test for the relationships among sedentary behavior, physical activity, and change in fundamental motor skills.

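### The plan sets out to test policy effects, but one regulated cohort measured twice gives one-year change, which mixes policy with ageing and secular change

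*Combined protocol and SAP*

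**What the plan says.** The analysis section states: "A repeated measures ANCOVA model will be used to test for effects of policy implementation on each dependent continuous variable". The four outcomes are in-care and total MVPA, and in-care and total screen-time. On adjustment it says "Covariates will include age, sex, BMI z-score, and sociodemographic characteristics", without saying at which visit these are taken. The Train Schedule lists BMI z-score and the parent survey at both baseline and follow-up.

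The causal purpose also appears in the Background, where the project is to "empirically test the effects of a health policy". Aim 2 is worded more descriptively, as behaviors "before and after the enactment of new state regulations".

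The design comes from several sections. Children are 3 or 4 years old and come from 10 centers (Inclusion and Exclusion Criteria). All study centers are licensed by the state Department of Education (Setting). Each child takes part for about one year (Number of Subjects and Subject Timeline). On the reach of the rule, A Carrot and Stick Approach says "new licensing standards will affect children attending over 1,300 licensed childcare centers state-wide".

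On timing, Specific Aims says the state "is implementing new regulations for children in childcare settings in 2015". A Carrot and Stick Approach says parish centers "must begin implementing changes by 2016 to renew their annual license" and places staff training in 2015-16. The Study Timeline puts baseline in May 2016 to April 2017 and follow-up in May 2017 to April 2018.

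**The concern.** Every child in the study is regulated, and every child gets a year older between the two visits. Policy, ageing and calendar time therefore move together, and the stated model has no term that separates them. Read as the plan words it, a change caused by age or by the calendar would count as a policy effect. The reverse is also possible: a real effect could be missed because part of it was already in place at baseline, or because ageing runs the other way. A larger sample would only narrow the interval around the mixed quantity.

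This matters because the project asks whether the policy benefits children and, if successful, plans to offer the findings to the region as a model for policy change.

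**Working it through.** **1. What the contrast contains.** Let P be the full policy effect, f the share already in place at baseline, A one year of ageing and S secular change. Mean change from baseline to follow-up is then (1 − f)P + A + S. Centered baseline age can explain why change differs between a 3-year-old and a 4-year-old. It leaves the year they both gain in the mean change.

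**2. The plan's own figure.** Power Analysis gives 266 children with 25% dropout: 266 × 0.75 = 199.5. The dropout step fits, since 199/0.75 = 265.3, rounded up to 266. Power, effect size, SD, within-child correlation and sidedness are not stated, so 266 cannot be rebuilt further. I use 200 completers below.

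**3. Drift with no policy effect.** The documents give no SD and no trend, so these inputs are assumed: SD of change 20 min/day, independent children, two-sided 5% normal test. SE = 20/√200 = 1.41. For a net shift δ = A + S, rejection probability = Φ(δ/SE − 1.96) + Φ(−δ/SE − 1.96).

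| Net shift, min/day | Declared a policy effect |
|---|---|
| 0.5 | 6% |
| 1 | 11% |
| 2 | 29% |
| 3 | 56% |
| 5 | 94% |

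At 3 min/day, SD 30 (SE 2.12) gives 29% and SD 15 (SE 1.06) gives 81%. A simulation with baseline age as a centered covariate (200 children, ages uniform on 3 to 5, SD 20, policy 0, ageing 3) gave a mean estimate of 2.99 and 55% rejection, so adjusting for baseline age did not remove the shift.

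**4. Effect partly in place at baseline.** Same assumptions, with P = 5 min/day and A + S = 0.

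| Share f in place | Contrast, min/day | Significant |
|---|---|---|
| 0% | 5 | 94% |
| 25% | 3.75 | 76% |
| 50% | 2.5 | 42% |
| 75% | 1.25 | 14% |
| 100% | 0 | 5% |

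With f = 50% and a net shift of −3, the contrast is 2.5 − 3 = −0.5, which has the wrong sign. With +3 it is 5.5.

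**5. The dates side by side.** Regulations are dated 2015, parish centers must begin changes by 2016, training is in 2015-16, and baseline runs May 2016 to April 2017. Even if the deadline means the end of 2016, January to April 2017 lies after it. Significance places re-evaluation one year after training and regulation. Counted from 2015-16, that can fall in the baseline window or run into the follow-up window, which opens in May 2017. No center-level dates are given, so overlap is possible but not shown.

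**6. Center.** Assume 20 completers in each of 10 centers and an ICC of change of 0.01, 0.05 or 0.10. The design effect 1 + 19 × ICC is 1.19, 1.95 or 2.90. A nominal 5% test that ignores center then rejects 2Φ(−1.96/√design effect) = 7%, 16% or 25% of the time with no shift at all.

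**7. Two possible alternatives.**
- *In-care minus out-of-care change in MVPA per waking hour.* Relative to the in-care change alone, its SE is √(1 + k² − 2rk), where k is the ratio of out-of-care to in-care SD and r their correlation. Over k = 0.5 to 1.5 and r = 0 to 0.7 this runs from √0.51 = 0.71 (k = r = 0.7) to √3.25 = 1.80 (k = 1.5, r = 0).
- *Age at each visit as a covariate.* With visits exactly one year apart, the age slope comes only from differences between children. With baseline age uniform on 3 to 5 (variance 1/3) and within-child correlation ρ, the variance of the time effect grows by the factor 1 + 3(1 + ρ)/[4(1 − ρ)]. The SE ratio is √1.75 = 1.32 at ρ = 0 and √3.25 = 1.80 at ρ = 0.5.

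**The case against.** Aim 2 only examines behaviors before and after, and the activity endpoints are worded as changes, so the analysis could be read as descriptive. That is fair to the aim, but the analysis section and the Background both use effect language.

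An implementation measure may also exist. Specific Aims asks "are the regulations being implemented as intended", and Procedures refers to a center observation under Aim 1, which the document does not otherwise describe. A between-center comparison is therefore possible in principle. The stated model does not include one, and there are only 10 centers. Because no model term is named, it remains an inference that the tested contrast is follow-up minus baseline.

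Age at visit could separate some ageing, because entry ages overlap with follow-up ages. This requires equal cross-sectional and within-child age slopes, which the plan does not state, and it leaves secular change in place.

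Two stronger readings are tempting. A reader might infer that baseline was post-policy, or that the planned one-year re-evaluation coincides with the baseline window. The dates do not establish either, and Specific Aims and Significance intend a pre-policy baseline. A reader might also infer that the result is biased by a known amount. The documents give no size or direction for ageing, secular change or prior exposure.

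**Conclusion.** The concern stands as a mismatch between the stated inference and the design. On the inference that the tested contrast is follow-up minus baseline, the planned analysis can support a statement about adjusted one-year change, but not about the effect of policy implementation. Bias is possible in either direction and is not quantified by the documents. The 56% figure (29% to 81%) illustrates how readily a modest drift would be declared a policy effect. It rests on an assumed SD, an assumed drift and independent children.

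A reader might infer that relabelling alone makes the result valid. It does not: the interval is valid for one-year change only if it also accounts for center. Independence is least plausible for in-care screen-time, which comes from classroom observation.

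**What to change.** In Primary Endpoints and Data Analysis Plan:

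1. Replace the effect wording with: *to estimate the adjusted change from baseline to 1 year*, for all four outcomes.
2. Use baseline values of age, BMI z-score and the parent-survey sociodemographic variables, all of which can be taken at either visit.
3. State that this change combines the regulations, the accompanying training and support, ageing and secular change, and is not an estimate of the policy effect.
4. Reconcile the dates in Specific Aims, A Carrot and Stick Approach, Significance and Study Timeline, and state that baseline may be partly post-policy. Each center's implementation and training dates, if they can be obtained, would show which baselines came first.
5. Account for center in the interval.

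The in-care minus out-of-care MVPA contrast may be added as exploratory. Its assumptions must be stated: equal ageing and secular change in and out of care, little policy spill-over outside care, and a fixed sleep and nap rule (no sleep log is listed). It does not extend to screen-time, where the in-care and out-of-care instruments differ. An age-at-visit model should not be used to claim a policy effect.

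The main changes need wording, a stated covariate time and an analysis that reflects center, with no new measurements on children. The price is a more modest conclusion.

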#### Inclusion Criteria:

- A child who is 3 or 4 years old
- Child spends at least 6 hours per day, 5 days per week at a participating childcare center
- Child will continue to attend the same childcare center for the next year

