### **Number of Subjects and Subject Timeline**

We plan to enroll 266 children. Each child will participate in the study for approximately 1 year. Surveys, anthropometric measures, fundamental motor skill assessments, and screen-time observations will take approximately 2 days to complete, and the child will be given an accelerometer to wear at home for 7 days at both baseline and 1 year follow-up. Staff members will spend approximately 2 weeks at each childcare center at baseline and 1 year follow-up to complete study procedures with each child.

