Fundamental Motor Skill Assessments. The Test of Gross Motor Development - 3rd edition (TGMD-3) and the Movement Assessment Battery for Children - 2nd edition (MABC-2) will be administered with the cooperation and support of the childcare center staff in small group settings. Groups of approximately 3-4 students will complete the assessments together. The TGMD-2 uses direct observation to evaluate performance on 13 skills including running, horizontal jumping, hopping, skipping, sliding, galloping, and balls skills (two-hand striking, one-hand striking, catching, kicking, overhand throwing, underhand throwing and dribbling). The TGMD-2 involves a trained administrator demonstrating the proper execution of the skill, and the participant is allowed one practice trial then two formal trials that will be evaluated. The MABC-2 examines eight tasks that are categorized as manual dexterity, balance, aiming and catching. This is a field-based assessment that examines correct performances on a variety of skills that are not evaluated by the TGMD-3 and will provide a holistic picture of children's motor abilities. These assessments will be audio and video recorded.

Physical activity. Physical activity and time spent in moderate to vigorous physical activity will be measured by a triaxial accelerometer (Actigraph GT3X+, Actigraph of Ft. Walton Beach, FL). Children will be measured on 7 full days during the baseline and follow-up periods. The child will be outfitted with the accelerometer on an elasticized belt, on the right mid-axillary line. The Actigraph is one of the most common accelerometers used for scientific purposes, and the GT3X+ version provides extensive data on steps/day and time spent in various activity intensities. Parents will be encouraged to have their child wear the accelerometer 24 hours per day for at least 7 days (plus an initial familiarization day and the morning of the final day), including 2 weekend days. During wear weeks, study staff will check accelerometry wear during school hours to assess for compliance. Accelerometer use will be documented and parents of children who do not have accelerometers on wear check days will be contacted via call, text, flyer, email, etc. as a reminder. The minimal amount of accelerometer data that will be considered acceptable is 4 days with at least 10 hours of

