### **Power Analysis**

A minimum of 266 children will be enrolled to ensure a well-powered study with significance level of  $\alpha = 0.05$  while allowing for a dropout rate of 25% between years 1 and 2. Estimation of change was based on data from Dowda et al., which observed a significant difference between MVPA in children in preschools rated low vs. high on physical activity environment.

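### The motor-skill associations are to be tested partly by correlations with no stated age adjustment or age-standardised score, so shared dependence on age can appear as an association among 3- and 4-year-olds

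*Combined protocol and SAP*

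**What the plan says.** All references are to the combined protocol and SAP.

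- **Objective.** After listing the primary endpoints, the section Primary Endpoints and Data Analysis Plan adds: "We will also assess the cross-sectional and longitudinal associations among sedentary behavior", and goes on to name physical activity and fundamental motor skills.
- **Method.** The last sentence of that section reads: "Correlations and a repeated measures ANCOVA will be used to test for the relationships among sedentary behavior, physical activity, and change in fundamental motor skills". The correlations are not described as partial, stratified, adjusted or unadjusted.
- **Covariates.** Age is named twice in the same section. "Age, sex, BMI z-score, and sociodemographic characteristics will be included as covariates" stands between the list of primary endpoints and the sentence on associations. "Covariates will include age, sex, BMI z-score, and sociodemographic characteristics" stands between the policy-effect ANCOVA and the sentence on correlations. Neither is expressly extended to the motor-skill analyses that follow it.
- **Age range.** The inclusion criterion is "A child who is 3 or 4 years old", so two children can differ by almost two years. On follow-up: "Each child will participate in the study for approximately 1 year".
- **Motor scores.** The section Procedures says that the TGMD-3 and MABC-2 "will be administered with the cooperation and support of the childcare center staff in small group settings" and describes the tasks and trials. It does not say which score is analysed. BMI, by contrast, is converted to a z-score using age and sex.

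**The concern.** A correlation, in the usual sense of the word, has no covariates. If older children in the sample score higher on motor tests and also differ in activity or screen time, the two measures will be correlated across the sample even when they are unrelated among children of the same age. A reader of the results could then take a developmental gradient for a link between behaviour and motor skill.

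The plan treats age as relevant elsewhere. It adjusts the activity and screen-time endpoints for age, and it standardises BMI for age and sex. The motor-skill correlations are the one place where the handling of age is left open. At stake is the interpretation of a declared additional analysis; the evaluation of the policy does not depend on it.

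**Working it through.** **1. The plan's own figure.** The Power Analysis section states: "A minimum of 266 children will be enrolled", allowing 25% dropout. 266 × 0.75 = 199.5, and 199 / 0.75 = 265.3, which rounds up to 266. The figure therefore agrees with about 199 completers. It concerns MVPA, and no sample size is given for the motor-skill associations. I use n = 266 (baseline) and n = 199 (follow-up).

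**2. Smallest correlation declared significant** (two-sided 5%; the plan gives α = 0.05 without sidedness): r = t / √(n − 2 + t²).
- n = 266: 1.969 / √(264 + 3.877) = 0.120
- n = 199: 1.972 / √(197 + 3.889) = 0.139

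**3. Correlation produced by age alone.** If skill and behaviour are unrelated at a given age and each depends linearly on age, then r(skill, behaviour) = r(age, skill) × r(age, behaviour).

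Both factors are assumptions, since the documents report neither: 0.3 to 0.6 for age with skill and 0 to 0.3 for age with behaviour. The product runs from 0 to 0.6 × 0.3 = 0.18.

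**4. How often the test then rejects.** Simulation with age uniform over the entry range, children independent, no association at fixed age, and 8,000 replicates per setting:

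| r(age, skill) | r(age, behaviour) | induced r | unadjusted, n = 266 | unadjusted, n = 199 |
|---|---|---|---|---|
| 0.3 | 0 | 0 | 5.5% | 5.1% |
| 0.6 | 0 | 0 | 4.3% | 5.2% |
| 0.3 | 0.1 | 0.03 | 8.0% | 7.5% |
| 0.5 | 0.1 | 0.05 | 13.0% | 11.0% |
| 0.5 | 0.2 | 0.10 | 38.2% | 29.1% |
| 0.6 | 0.2 | 0.12 | 49.9% | 38.5% |
| 0.5 | 0.3 | 0.15 | 70.0% | 57.0% |
| 0.6 | 0.3 | 0.18 | 84.8% | 73.2% |

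The age-partial correlation rejected in 4.4% to 5.5% of replicates over all settings run. That is simulation noise around 5%: the standard error is √(0.05 × 0.95 / 8000) = 0.24 percentage points.

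**5. Cross-check by Fisher z.** The mean of the test statistic is atanh(r) × √(n − 3). For r = 0.18 and n = 266 it is 0.182 × √263 = 2.95, so the rejection probability is Φ(2.95 − 1.96) = 0.84, in line with the simulated 84.8%.

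**6. Change scores.** The table describes skill level. For one-year change, the first factor becomes r(age, change). All children are followed for about the same time, so this is zero unless the rate of gain differs by age. If younger children gain more, it is negative, and with a behaviour that rises with age the induced correlation is negative too. The documents give nothing from which to size this, so I give no rate for it.

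**The case against.** The strongest reply is that the plan is silent on adjustment, and silence is not a decision to leave age out. Age is in the only covariate list the section contains, and that list is repeated immediately before the sentence on correlations. The same sentence pairs the correlations with an ANCOVA, which by its nature carries covariates and may well include age. The scoring scale is also unstated, and age-standardised motor scores would remove most of the cross-sectional problem. Finally, the documents say neither that motor skill rises steeply with age in this range nor that activity or screen time varies with age. Both are needed, and if either dependence is absent the test keeps its 5% level.

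Most of this stands, and it rules out several stronger readings that a reader might infer:

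- That the plan has chosen raw scores. The Procedures section describes how the tests are administered and does not name the score to be analysed.
- That a false positive association is bound to arise. It can arise, under conditions that the documents do not establish.
- That the question on associations cannot be answered. An age-adjusted ANCOVA would go some way to answering it.
- That the percentages apply to change in motor skills, which is what the quoted sentence names. They apply to the cross-sectional associations.

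The reply does not remove the gap itself. Both covariate sentences come before the motor-skill text and follow other analyses. Applying them to the correlations requires wording that is not there, and taken at face value the correlations are unadjusted.

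**Conclusion.** The point holds as a conditional weakness in an additional analysis. With 266 children, an unadjusted cross-sectional correlation between raw motor scores and a behaviour has a false-positive rate of about 5% to 85% under the assumed ranges; with 199 it is about 5% to 73%. The lower end applies when the behaviour is unrelated to age. A middle case (0.5 and 0.2) gives 38% at 266. These rates rest on age correlations that are assumed, on raw scores being analysed, and on no adjustment being made. For the change analysis the size is unknown and the sign could go either way.

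A reader might extend this to the policy evaluation. The documents do not support that: the policy-effect ANCOVA names age as a covariate, motor skills are not among the listed primary endpoints, and Specific Aim 2 does not mention them. The reason to act is that the remedy is almost free.

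**What to change.** In the last sentence of Primary Endpoints and Data Analysis Plan:

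1. Replace the correlations with partial correlations or regression adjusted for exact age at the test date and for sex, in both the cross-sectional and the change analyses.
2. State that the age covariate also applies to the motor-skill ANCOVA.
3. State which motor score is analysed and, where an age-standardised score is available, report it beside the raw score.

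Date of birth and sex are already collected in the parent survey, so age at testing needs only the test date. The cost is two degrees of freedom. At n = 266 the smallest significant correlation moves from 0.120 to 1.969 / √(262 + 3.877) = 0.121. No new data or visits are needed.
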